### 3. Age and Reproductive Status

- a) Men and women, ages  $\geq$  18 years (or age of majority)
- b) Women of childbearing potential (WOCBP) must have a negative serum or urine pregnancy test (minimum sensitivity 25 IU/L or equivalent units of HCG) within 24 hours prior to the start of study drug.
- c) Women must not be breastfeeding and must agree not to breastfeed during the study and for 100 days thereafter
- d) WOCBP must agree to follow instructions for method(s) of contraception for the duration of treatment with study drug plus 5 half-lives of study drug (70 days) plus 30 days (duration of ovulatory cycle) for a total of 100 days post-treatment completion.
- e) Males who are sexually active with WOCBP must agree to follow instructions for method(s) of contraception for the duration of treatment with study drug, plus 5 half-lives of the study drug (70 days) plus 90 days (duration of sperm turnover) for a total of 160 days post-treatment completion.
- f) Azoospermic males and WOCBP who are continuously not heterosexually active are exempt from contraceptive requirements. However they must still undergo pregnancy testing as described in this section.

Investigators shall counsel WOCBP and male subjects who are sexually active with WOCBP on the importance of pregnancy prevention and the implications of an unexpected pregnancy. Investigators shall advise WOCBP and male subjects who are sexually active with WOCBP on the use of highly effective methods of contraception. Highly effective methods of contraception have a failure rate of  $< 1\%$  when used consistently and correctly.

At a minimum, subjects must agree to the use of **two methods** of contraception, with one method being highly effective and the other method being either highly effective or less effective as listed below:

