### **6.1.1      *Serious Adverse Event Collection and Reporting***

Sections 5.5.1 in the Investigator Brochure (IB) represent the Reference Safety Information to determine expectedness of serious adverse events for expedited reporting. Following the subject's written consent to participate in the study, all SAEs, whether related or not related to study drug, must be collected, including those thought to be associated with protocol-specified procedures. All SAEs must be collected that occur during the screening period and within 85 days of discontinuation of the Treatment Period. If applicable, SAEs must be collected that relate to any later protocol-specified procedure (eg, a follow-up skin biopsy).

The investigator must report any SAE that occurs after these time periods and that is believed to be related to study drug or protocol-specified procedure.

An SAE report must be completed for any event where doubt exists regarding its seriousness.

If the investigator believes that an SAE is not related to study drug, but is potentially related to the conditions of the study (such as withdrawal of previous therapy or a complication of a study procedure), the relationship must be specified in the narrative section of the SAE Report Form.

SAEs, whether related or not related to study drug, and pregnancies must be reported to BMS (or designee) within 24 hours of awareness of the event. SAEs must be recorded on the SAE Report Form; pregnancies on a Pregnancy Surveillance Form (electronic or paper forms). The preferred method for SAE data reporting collection is through the eCRF. The paper SAE/pregnancy surveillance forms are only intended as a back-up option when the eCRF system is not functioning. In this case, the paper forms are to be transmitted via email or confirmed facsimile (fax) transmission to:

**SAE Email Address:** Refer to Contact Information list.

**SAE Facsimile Number:** Refer to Contact Information list.

For studies capturing SAEs through electronic data capture (EDC), electronic submission is the required method for reporting. In the event the electronic system is unavailable for transmission, paper forms must be used and submitted immediately. When paper forms are used, the original paper forms are to remain on site.

**SAE Telephone Contact** (required for SAE and pregnancy reporting): Refer to Contact Information list.

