2 STUDY DESCRIPTION

2.1 Study Design

This is an exploratory, randomized, single-blinded assessment study in subjects with early RA defined as symptoms of RA for no more than 12 months prior to screening and satisfying the criteria for RA according to the ACR/EULAR 2010 classification at some point during the 12-month period. Eligible subjects must have been on methotrexate (MTX) for at least 12 weeks with a stable dose of MTX for at least 28 days prior to randomization and are naive to biologic DMARD. The study consists of a screening period of up to 28 days, followed by a 24-week single-blind treatment period with abatacept or adalimumab, followed by a 24-week open-label treatment period with abatacept, followed by an 85-day follow-up period.

Eligibility will be based on specified inclusion and exclusion criteria, medical history, disease activity and safety assessments. Randomization must occur within 28 days of signing the informed consent.

On Day 1, subjects will be randomized to one of two parallel treatment arms in a 1:1 ratio:

- abatacept SC (125mg) weekly
- adalimumab SC (40mg) once every two weeks

All subjects continuing in the open-label treatment period will receive abatacept 125mg SC, weekly. Those subjects randomized to adalimumab will switch to abatacept at Week 28 following a six week washout period. The dose of methotrexate must remain stable throughout the study and may only be lowered due to intolerance or adverse event. Subjects not wishing to continue on open-label abatacept have the option of discontinuing treatment at the end of the single-blind period and proceeding to the post-treatment follow-up period.

Subjects who discontinue treatment of study drug or complete the study will have one follow-up visit 85 days after the last dose of investigational product to perform safety assessments.

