6 STUDY PERIODS, TREATMENT REGIMENS AND POPULATIONS FOR ANALYSES

6.1 Study Periods

The following periods are defined for this statistical analysis plan:

- The pre-treatment period covers the time period prior to or on the first dose time of single-blind study medication.
- The single-blind treatment period starts at the time of the first dose of single-blind study medication and lasts until :
 - the time of the last dose of single-blind study medication for concomitant medication summaries
 - 56 days post last dose of single-blind study medication for subjects who do not enter OL. For those subjects who do enter OL, the single-blind treatment period lasts until first day of open-label for abatacept randomized subjects or until 10 days post last dose of single-blind treatment for adalimumab randomized subjects for safety analyses (AE and labs).
 - 21 days post last dose of single-blind study medication for subjects who do not enter OL For those subject who do enter OL, the single-blind treatment period lasts until first day of open-label for abatacept randomized subjects or until 10 days post last dose of single-blind treatment for adalimumab randomized subjects for immunogenicity analyses

Note: To align the cut-off of the single-blind treatment period for abatacept and adalimumab and taking into account that for adalimumab there is a wash-out period of 6 weeks, 10 days is

used to cut the single-blind treatment period for adalimumab. Ten (10) is equal to the expected maximum number of days after last single-blind abatacept dose and prior to first open-label abatacept dose (7 days +/- 3 days).

- The open-label abatacept treatment period starts at the time of the first dose of open-label abatacept treatment and lasts until 56 days post last open-label abatacept dose (AE and labs), except for immunogenicity analyses for which the open-label period goes up to 21 days post last open-label abatacept dose.
- The cumulative abatacept period starts at the time of the first dose of abatacept (single-blind or open-label) and lasts until 56 days post last abatacept dose (single-blind or open-label), except for immunogenicity analyses for which the cumulative abatacept period goes up to 21 days post last abatacept dose.

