7.7.2.3 Autoimmune Disorders

The frequency of pre-specified autoimmune disorders, defined using a BMS customized SMQ, occurring during the single-blind treatment period will be provided. Autoimmune disorders occurring during the single-blind treatment period will be summarized by severity. All reported autoimmune disorders occurring during the single-blind treatment period will be listed.

Similar summaries and listings will be done for the cumulative abatacept period.

7.7.2.4 *Injection Adverse Events*

A. Systemic Injection Reactions (pre-specified, defined using a BMS customized SMQ) are defined as systemic AEs (such as hypersensitivity reactions) occurring during the first 24 hours after abatacept/adalimumab SC administration.

B. Local Injection Site Reactions (pre-specified, defined using a BMS customized SMQ) are defined as those AEs that occur at the site of SC injection.

The pre-specified systemic injection reactions and local injection site reactions occurring during the single-blind treatment period will be summarized by severity. These AEs will also be listed.

In addition, a pre-specified local injection site reaction event of interest, defined as the AEs with the following PT that occur at the site of SC injection: *Erythema, Pain, Pruritus, Haematoma, and Swelling* will be summarized by severity.

Similar summaries and listings will be done for the cumulative abatacept period.

7.7.3 *Deaths*

All AEs with the outcome of death reported during the single-blind treatment period will be listed by treatment group, together with a clinical narrative relating to the death of the subjects.

A similar listing will be done for the cumulative abatacept period.

7.7.4 *Other Serious Adverse Events*

SAEs are captured on a CRF page. All SAEs occurring during the single-blind treatment period will be summarized by treatment group and listed.

Similar summaries and listings will be done for the cumulative abatacept period.

7.7.5 *Adverse Events Leading to Discontinuation of Study Therapy*

AEs leading to discontinuation of study drug are identified as those AEs with an action code of 5 on the eCRF page (5 = discontinued study drug). All such AEs occurring during the single-blind treatment period will be listed and summarized by SOC, PT and treatment group. In addition, a listing of subjects with SAEs leading to discontinuation will be provided.

Similar summaries and listings will be done for the cumulative abatacept period.

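### SAP safety summaries stop 56 days after the last dose, so deaths, SAEs and malignancies arising on Days 57–85 of the 85-day follow-up enter no summary count

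*SAP*

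**What the plan says.** **Collection.** Protocol 6.1.1 states: "All SAEs must be collected that occur during the screening period and within 85 days of discontinuation of the Treatment Period". Protocol 6.1 requires cancer to be handled as an SAE, so malignancies fall under the same rule. Protocol Table 5.1-3 schedules an AE assessment 85 days after the last dose. SAP 2.1 keeps that visit: subjects who stop or complete "will have one follow-up visit 85 days after the last dose of investigational product to perform safety assessments".

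**Reporting commitment.** Protocol 8.4.3 commits to frequency distributions and listings covering every AE, death and SAE, without a cut-off after the last dose.

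**Analysis periods.** SAP 6.1 sets these ends for AE and laboratory analyses:
- single-blind period, subjects not entering open label: "56 days post last dose of single-blind study medication for subjects who do not enter OL";
- single-blind period, adalimumab subjects who do enter open label: "until 10 days post last dose of single-blind treatment for adalimumab randomized subjects for safety analyses (AE and labs";
- open-label period: "lasts until 56 days post last open-label abatacept dose (AE and labs";
- cumulative abatacept period: "lasts until 56 days post last abatacept dose (single-blind or open-label), except for immunogenicity analyses".

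**Outputs.** SAP 7.7.1 summarizes AEs for the single-blind and cumulative abatacept periods. SAP 7.7.2.2 (malignancy), 7.7.3 (deaths) and 7.7.4 (SAEs) use the same two periods. For deaths the text is: "All AEs with the outcome of death reported during the single-blind treatment period will be listed by treatment group", with a similar listing for the cumulative period.

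**Out-of-period AEs.** SAP 7.7.1 has one sentence on AEs regardless of timing. As it stands it is incomplete. It sends such AEs to a comprehensive listing described earlier in the section, but that listing is itself defined by the two periods.

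**The concern.** The data are collected to Day 85 and the protocol promises to tabulate all deaths and SAEs, yet no SAP summary covers the last 29 days. The SAP gives no reason for leaving late deaths, SAEs and malignancies out of the counts. A 56-day window is a natural choice for common AEs and laboratory values. It suits rare, serious and possibly late-diagnosed events less well, because each one matters individually in a trial of this size.

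At stake is the completeness of three outputs that safety readers consult first: the death listing, the SAE table and the malignancy table. Applied literally, the plan leaves a new event on, say, Day 70 out of all three, although it is on the CRF.

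Adalimumab subjects who never enter open label are the most exposed. They are outside the cumulative abatacept population (SAP 6.3), so no other period can pick up their late events.

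**Working it through.** **1. Reproduce the 56 days.** SAP 7.4.1 describes the 56-day offset as about four abatacept half-lives. Protocol 3.3.1, item 3(d), gives "5 half-lives of study drug (70 days"), which implies 70 / 5 = 14 days per half-life. Then 4 × 14 = 56 days. The figure reproduces exactly, so the window is deliberate.

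**2. Size of the gap per subject.**
- Uncounted days: 85 − 56 = 29.
- Share of post-dose follow-up: 29 / 85 = 34%.
- For a subject whose last abatacept dose is on Day 162 (Protocol 4.5.1) and who does not enter open label, observation runs to Day 162 + 85 = 247, and 29 / 247 = 12% of it is uncounted.

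The protocol's SAE window runs from the end of the Treatment Period, and the follow-up visit has a margin of 10 days either way, so the gap can be slightly longer than 29 days.

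**3. Person-time.** N × 29 / 365.25, with N from SAP 5 (25 per arm, later 40 per arm):
- N = 50: 50 × 29 / 365.25 = 3.97 patient-years;
- N = 80: 80 × 29 / 365.25 = 6.35 patient-years.

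Both are upper bounds. They assume that every subject is treated and followed to Day 85 after the final dose.

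**4. Expected uncounted SAEs.** The documents give no SAE rate, so the rates below are assumptions. Expected number λ = rate × patient-years; the chance of at least one is 1 − exp(−λ).

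| Assumed SAEs per 100 patient-years | λ, N = 50 | At least one | λ, N = 80 | At least one |
|---|---|---|---|---|
| 2 | 0.08 | 8% | 0.13 | 12% |
| 5 | 0.20 | 18% | 0.32 | 27% |
| 10 | 0.40 | 33% | 0.64 | 47% |
| 20 | 0.79 | 55% | 1.27 | 72% |

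**5. Where the gap falls.**
- *Never enters open label, either arm:* Days 57–85 follow the last single-blind dose. The between-arm single-blind summary loses them. For abatacept subjects the cumulative period ends on the same day, so it does not recover them.
- *Enters open label:* Days 57–85 after single-blind dosing generally fall inside the cumulative abatacept period. The gap comes after the last open-label dose and affects only the pooled abatacept summary.

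Adalimumab subjects who enter open label also have an earlier single-blind cut, 10 days in SAP 6.1 but 20 days in SAP 7.7.1. That is a separate inconsistency and is not included in these figures.

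**6. Does any listing cover the gap?** The washout listing in SAP 7.7.1 is limited to adalimumab subjects treated with open-label abatacept, and stops at their first open-label dose. The incomplete sentence may be meant to cover the gap, but the listing it points to is bounded by the same periods. SAP 7.7 speaks generally of individual AE listings; 7.7.3 and 7.7.4 are specific and contain no exception for late events.

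**The case against.** **The window is principled.** It rests on about four half-lives and matches the exposure offset, and collecting data for longer than the on-treatment summary window is not an error in itself. This stands for common AEs, laboratory values and exposure-adjusted rates. It does not explain why no summary at all covers the rest of the collection period for deaths, SAEs and malignancies. The rationale also concerns abatacept, while the cut is applied to adalimumab subjects as well.

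**Late events may be listed.** A reader might infer that Day 57–85 events go unreported. The documents do not support that. The surviving words of the sentence in SAP 7.7.1 and the general promise of AE listings in SAP 7.7 suggest that out-of-period AEs are kept on a listing, and the missing words may be lost text. What stands is that such events are uncounted and that the scope of the listing is unclear.

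**Many late outcomes would still be caught.** A reader might infer that a subject who stops for an infection and dies on Day 70 disappears. Probably not: the infection began within the period, AEs are listed by onset date, and Protocol 6.1.1 requires SAEs to be followed to resolution or stabilization. The fatal outcome would plausibly reach the death listing, although it is ambiguous there whether onset, outcome or reporting must fall in the period. The firm gap concerns events with onset on Days 57–85.

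**The 70 days is not an AE window.** It sets contraception duration, so it is not a reason in itself to extend the AE tables. Accepted; it is used above only to check the half-life.

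**Unseen sources.** SAP 7.7 defers to sponsor safety conventions that are not supplied. The 85-day SAE rule comes from the original protocol, whereas the SAP follows later amendments. The SAP does repeat the 85-day safety visit, and nothing available shows that the conventions extend the counts.

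**Conclusion.** The mismatch is real and limited. As written, deaths, SAEs and malignancies with onset on Days 57–85 after the final dose enter no summary count; at best they appear on a general AE listing. The gap is 29 of 85 days (34%), at most 4.0 patient-years for 50 subjects or 6.4 for 80. At assumed rates of 2 to 20 SAEs per 100 patient-years that is roughly 0.1 to 0.8 SAEs for 50 subjects and 0.1 to 1.3 for 80.

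A reader might go further and infer that the gap would change the comparison between abatacept and adalimumab. The documents do not support that. Only subjects who never enter open label contribute to the between-arm gap, and their number is not given. AE frequencies are not tested, and the trial is exploratory. For everyone else the gap affects the pooled abatacept summary.

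The conclusion assumes that the 85-day SAE rule survived the amendments and that the sponsor's conventions do not already cover the period. It is a cheap improvement, not a flaw that undermines the analysis.

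**What to change.** - **SAP 7.7.2.2, 7.7.3 and 7.7.4:** in addition to the planned outputs, report malignancies, deaths and SAEs through the 85-day collection period, by treatment received. Show events after Day 56 as a flagged row or listing, so that the planned counts stay visible. Say whether a death is placed by the onset of the fatal event or by the date of death.
- **SAP 6.1 and 7.4.1:** leave the 56-day window and exposure offset unchanged for common-AE, laboratory and exposure-adjusted tables. The AE summaries are proportions of treated subjects, so the flagged rows need no new denominator.
- **SAP 7.7.1:** complete the sentence on out-of-period AEs so that it excludes them from the AE frequency tables but includes them in the AE, SAE and death listings, and define the comprehensive listing to match.

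Cost: SAP wording and a flag in three outputs, using data already collected. The downside is two cut-offs to footnote and possibly slightly higher SAE counts.

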7.7.1 Adverse Events

All AEs are coded and grouped into Preferred Terms (PT) by System Organ Class (SOC), using the latest approved version of the Medical Dictionary for Regulatory Activities (MedDRA) at the time of database lock. Listings and summaries will be based on the resulting SOCs and PTs.

All reported AEs during the single-blind treatment period and all reported AEs reported during the cumulative abatacept period will be listed, indicating the subjects id, age, gender, the date of onset, the day of onset relative to the start of treatment, investigator's assessment of severity and relationship to study drug.

In addition, all reported AEs during the washout-out period (beyond 20 days past last single blind dose of adalimumab up to first dose of open-label abatacept) will be in a separate listing. This listing will only include adalimumab patients who are treated with OL abatacept. The threshold of 20 days is chosen for this listing, because AEs up to 20 days past last single-blind dose of adalimumab are included in the AE summaries of the single-blind period. It should be noted that for the single-blind analysis a threshold of 20 days (post-hoc) was used instead of 10 days defined in version 1.0 of SAP.

AEs will be summarized for the single-blind treatment period and the cumulative abatacept period. This period is defined in [Section 6.1](#). These AE summaries will be based on proportions, which represent the number of subjects experiencing the AEs divided by the number of subjects who received at least 1 dose of single-blind study medication for the Week 24 analysis and by the number of subjects treated with abatacept for the cumulative abatacept period analysis.

Any AEs irrespectively of when they occur, but will appear on the above mentioned comprehensive listing.

Summary information (the number and percent of subjects by treatment) will be tabulated for the following AEs:

- all AEs including clinical and laboratory AEs
 - most common AEs (reported in 10% of subjects or more in any treatment group)
 - categorized by severity
- related events
 - most common (reported in 5% of subjects or more in any treatment group)
 - categorized by severity
- serious adverse events (SAEs)
- discontinuations due to SAEs/AEs

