8.5 Day Ranges for Analysis of Time Points

Single -blind period

Subjects do not always adhere strictly to the visit schedule timing in the protocol. Therefore, the designation of visits during the single-blind period of the study will be based on the day of evaluation relative to the trial (day of first single-blind study medication = study Day 1) rather than the nominal visit recorded in the CRF. Mutually exclusive relative day windows are defined below to provide derived visits that correspond to the post-baseline time points. If a visit falls outside the pre-specified visit windows, then the data collected at that visit will not be assigned a derived visit but will remain in the derived data sets. Determination of baseline values is addressed in

Section 8.2. The day ranges for assessments during the single-blind treatment period are presented in Table 8.5-1.

Table 8.5-1: Day Ranges for Assessments during Single-Blind Treatment Period

| Visit | Target Day | Assessments |
|------------------|------------|-------------|
| Screening | < 1 | < 1 |
| Day 1 (Baseline) | 1 | 1* |
| Week 4 | 29 | 8 - 43 |
| Week 8 | 57 | 44 - 85 |
| Week 16 | 113 | 86 - 141 |
| Week 24 | 169 | 142 - 211 |

* Note: See [Section 8.3](#) for baseline measures.

For subjects who receive single-blind abatacept and continue into the open-label treatment period, the upper limit of Week 24 window is first dose day of the open-label period. For subjects who receive single-blind adalimumab and continue into the open-label treatment period, the upper limit of this window is the last dose of single-blind study medication + 10 days.

Open-label period

The day ranges for assessments during the open-label period are presented in Table 8.5-2.

Table 8.5-2: Day Ranges for Assessments during Open-label Period

| Visit | Target Day | Assessments |
|---------|------------|----------------|
| Week 28 | 197 | Day 2 OL - 211 |
| Week 32 | 225 | 212 - 253 |
| Week 40 | 281 | 254 - 309 |
| Week 48 | 337 | 310 - 365 |

Efficacy and biomarker assessments performed beyond 42 days after the last dose are excluded.

Lab assessment performed beyond 56 days after the last dose are excluded.

If a subject has more than 1 visit where a measurement is recorded within a window, the measurement closest to the target day will be used. In case of 2 visits being equidistant from the target, the later measurement will be used in analyses.

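### SAP 8.5 closes the Week 24 window of adalimumab open-label entrants at last dose + 10 days, which shuts out its own target, Day 169; SAP 7.7.1 reports 20 days

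*SAP*

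**What the plan says.** SAP 8.5 assigns visits by day of evaluation "rather than the nominal visit recorded in the CRF". Table 8.5-1 gives Week 24 a target of Day 169 and a general range of Days 142 to 211. Subjects who go on to open label have a different upper limit. For abatacept it is the day of the first open-label dose. For adalimumab, "the upper limit of this window is the last dose of single-blind study medication + 10 days". If a visit fits no window, "then the data collected at that visit will not be assigned a derived visit but will remain in the derived data sets". Section 8.5 also sets an outer limit: "Efficacy and biomarker assessments performed beyond 42 days after the last dose are excluded".

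SAP 6.1 applies the same 10 days to the end of the single-blind period for adalimumab entrants: "until 10 days post last dose of single-blind treatment for adalimumab randomized subjects for safety analyses (AE and labs", and "until 10 days post last dose of single-blind treatment for adalimumab randomized subjects for immunogenicity analyses". Its note derives the 10 from weekly abatacept dosing, 7 + 3. SAP 7.4.1 uses + 10 in the adalimumab exposure formula.

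SAP 7.7.1 gives another number. It says that "AEs up to 20 days past last single-blind dose of adalimumab are included in the AE summaries of the single-blind period", and that "a threshold of 20 days (post-hoc) was used instead of 10 days defined in version 1.0 of SAP". The same section still sends the reader to 6.1 for the definition of the period.

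**The concern.** The 10 days belongs to a weekly regimen. Adalimumab is given every 14 days, and its last single-blind dose is scheduled at Week 22, about two weeks before the Week 24 visit. A cut at 10 days therefore falls between the last dose and the visit it should include.

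SAP 7.1 puts the focus of the exploration on Day 169, and apart from responder rates its analyses use available data only. A Day 169 measurement without a derived visit drops out of the Week 24 summaries. This would happen in the adalimumab arm alone. The adalimumab result at Day 169 would then rest on subjects who did not enter open label and on entrants whose last dose was late, a group selected after randomization.

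Under 6.1 the Week 24 laboratory values of these entrants, and any immunogenicity sample taken at that visit, would also fall after the end of the single-blind period. If 6.1 governs adverse events too, events 11 to 20 days after the last adalimumab dose are in neither the single-blind summaries nor the washout listing in 7.7.1, which starts beyond day 20.

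**Working it through.** **Inputs.** Week 24 target Day 169, range 142 to 211, and the + 10 limit (SAP 8.5). Switch at Week 28 after a six-week washout (SAP 2.1). Adalimumab every 14 days from Day 1 up to Week 22, printed as Day 152 (Protocol 4.5.2). Visit tolerance of ±3 days (Protocol Table 5.1-2, footnote a). Dose window of ±7 days (Protocol 4.5.2.2). The protocol supplied is the original, before the extension.

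**The plan's own figures.** Study day of week w = 1 + 7w. Week 24 = 1 + 168 = 169 and Week 28 = 1 + 196 = 197, as printed. The cut-off reproduces as 7 + 3 = 10.

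**Last adalimumab dose on target.** By 14-day steps: 1 + 14 × 11 = 155. By the washout: 197 − 42 = 155. The printed Day 152 does not agree with these. The passages must be reconciled, so both days are carried through.

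**Upper limit of the Week 24 window = last dose + cut-off.**

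| | Last dose Day 155 | Last dose Day 152 |
|---|---|---|
| Limit at + 10 | 165 | 162 |
| Week 24 window at + 10 | 142 to 165 | 142 to 162 |
| Visit days 166 to 172 inside | 0 of 7 | 0 of 7 |
| Limit at + 20 | 175 | 172 |
| Visit days 166 to 172 inside | 7 of 7 | 7 of 7 |

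**Does another window take the visit?** No. The Week 28 window in Table 8.5-2 opens on the second open-label day, which is Day 198 if open label starts on Day 197.

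**The other groups.** Abatacept on target: last dose 1 + 7 × 23 = 162, first open-label dose 162 + 7 = 169, so Day 169 is inside. Adalimumab non-entrants: the window runs to Day 211, and Day 169 is 169 − 155 = 14 or 169 − 152 = 17 days after the last dose, within 42.

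**Off-target last doses.** At + 10, a Day 169 visit is kept only from a last dose on Day 169 − 10 = 159, which is 4 days late from Day 155 or 7 days late from Day 152. A Day 166 visit is kept from Day 156. At + 20, a Day 169 visit is kept from Day 149 and a Day 172 visit from Day 152.

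**Exposure under 7.4.1** (last + offset − first). Last dose Day 155: 155 + 10 − 1 = 164 days, or 174 at + 20. Last dose Day 152: 161 or 171. On-target abatacept: 169 − 1 = 168. If adverse events are counted to + 20 but exposure to + 10, the rate is inflated by 174/164 = 1.061 or 171/161 = 1.062, about 6%, for an on-target entrant. This is conditional, because SAP 7.7.6 leaves exposure to the sponsor's standard algorithms.

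**The case against.** Only 8.5 defines the Week 24 window. Section 6.1 covers adverse events, laboratory data and immunogenicity, and 7.4.1 covers exposure. A reader might infer that all three remove Day 169 efficacy and biomarker data. They do not: that loss rests on one sentence in 8.5. The other two sections matter as part of the unreconciled 10 against 20.

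The sponsor evidently noticed the 10-day cut. Section 7.7.1 says in the past tense that 20 days was used for the single-blind analysis. If that covered every single-blind analysis, 8.5 is merely out of date and nothing was lost. This stands as a limit on the harm. A reader might infer that adalimumab Day 169 values were in fact dropped, or that the reported comparison is biased. The documents support neither inference, because they do not show which value was programmed.

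The reverse inference, that 20 days is already the rule everywhere, is no better supported. Section 7.7.1 sits under adverse events, gives no derivation for 20, and refers back to a definition that says 10.

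The 0 of 7 result holds for an on-target last dose. The protocol's dose window allows late doses that bring some visits back inside. That is correct, but a window that keeps its target visit only when dosing is late is still wrong. The trial is also exploratory with no primary endpoint, which lowers the stakes but does not resolve the contradiction.

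**Conclusion.** The point holds as an error in the text of 8.5. For adalimumab open-label entrants dosed on target, the Week 24 window ends 169 − 165 = 4 days before its target (last dose Day 155) or 169 − 162 = 7 days before it (Day 152). Followed literally, this takes away one of the four post-baseline visits in Table 8.5-1 in one arm only. The 20 days in 7.7.1 contradicts the 10 in the 6.1 definition it refers to, and the SAP does not say which analyses moved.

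The result assumes an on-target last dose and the ±3-day visit tolerance of the original protocol. Confidence is high for the textual conflict. Actual data loss is unknown. The size and direction of any bias cannot be computed, because neither the programmed value nor the proportion entering open label is visible. The SAP should be corrected.

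**What to change.** 1. In 8.5, replace + 10 for adalimumab open-label entrants with a limit that contains Day 169, and keep windowing by day of evaluation. The sponsor's own + 20 does this for an on-target last dose.
2. In 6.1, change the adverse-event cut-off to the 20 days that 7.7.1 says was used. State one cut-off for laboratory data and immunogenicity that includes the Week 24 visit. Using 20 there as well is a choice to be stated, not something 7.7.1 settles.
3. In 7.4.1, make the exposure offset match the adverse-event cut-off wherever rates per patient-year use that exposure.
4. Record which value each Week 24 analysis used, and re-run those tables only if + 10 was programmed.

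The cost is SAP wording and possibly a re-run; no new data are needed. There is a trade-off against the alignment sought in the 6.1 note. Relative to a nominal abatacept end at Day 169, the adalimumab period goes from 4 days short to 6 days over (last dose Day 155), or from 7 short to 3 over (Day 152). Under + 20 some visits after a permitted early last dose would still fall outside, for example a Day 169 visit after a last dose on Day 148.
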